2. Day 25 visit ( $\pm$  5 days) should be performed during Cycles 2, 4, 6, 9 and every approximately 12 weeks thereafter (Cycles 12, 15, etc.) until disease progression.
3. An End of Treatment visit will be conducted within 30 days ( $\pm$  7 days) from the last dose of tipifarnib or immediately before the initiation of any other anticancer therapy.
4. Follow up visit required only for subjects who terminated treatment for reasons other than death or disease progression.
5. Information on subject's survival and use of subsequent anticancer therapy may be collected by phone. Upon disease progression, all subjects will be followed approximately every 12 weeks for survival and the use of subsequent therapy until either death or 12 months after accrual in the subject's study cohort has been completed, whichever occurs first.
6. Medical history is to include demographics, primary diagnosis and WHO classification, outcome and duration of response to prior cancer therapy and any ongoing AEs
7. Assessed throughout the course of the treatment and approximately 30 days after treatment discontinuation. Additional assessments may be performed until AE resolution or the AE is deemed irreversible by the Investigator.
8. Assessment to be performed within 14 days of Cycle 1 Day 1
9. In women with childbearing potential, pregnancy tests (urine or serum) will be conducted at screening (must be performed within 72 hours of Cycle 1 Day 1), on Day 1 of each treatment cycle beginning at Cycle 2 and at the End of Treatment visit. If a positive urine pregnancy test is obtained, a confirmatory serum pregnancy test should be conducted.
10. Assessment to be performed within 72 hours of Cycle 1 Day 1.
11. Assessment to be performed beginning at Cycle 2.

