Each cohort has a 2-stage design. Seven subjects will be enrolled in the first stage of each cohort. If at least one objective response is observed, the cohort will be expanded to enroll an additional 11 subjects in stage 2. The cohort will be considered positive if 4 or more responses are observed in the 18 subject cohort ([Figure 1](#)). Based on the absence of objective responses observed in the initial cohort of RAS mutant CMMML subjects, all enrolled subjects enrolled in amendment 3 cohorts 1-4 will have RAS wild type tumor status at study entry.

Only consented subjects who meet all eligibility criteria will be enrolled in the study. Screening evaluations will be completed within 4 weeks (28 days) of Cycle 1 Day 1. Any screening evaluation, including disease status, will need to be repeated if performed more than 4 weeks from Cycle 1 Day 1. Evaluations performed as part of the standard of care within 28 days of dosing but prior to consent, do not need to be repeated. By signing the consent form, study subjects agree to the collection of standard of care health information.

Subjects (amendment 3 cohorts 1-4) will receive tipifarnib administered at a dose of 400 mg, orally with food, bid for 21 days in 28 day cycles. Food intake is important for tipifarnib bioavailability. The relevance of food intake with tipifarnib administration should be highlighted to study subjects. Subjects may use proton pump inhibitors or H2 antagonists during the treatment portion of this study. However, subjects should be instructed to use antacids (magnesium or aluminum containing products) at least 2 hours before or after intake of oral study drug.

Stepwise 100 mg dose reductions to control treatment-related, treatment-emergent toxicities are indicated in the body of the study protocol. In the absence of unmanageable toxicities, subjects may continue to receive tipifarnib treatment until disease progression. In the absence of unmanageable toxicities, subjects may continue to receive tipifarnib treatment until disease progression. Provisions will be made for the continuation of study treatment in subjects whose disease has not progressed beyond the end of the study, e.g. a single patient treatment protocol.

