Subjects who terminate treatment for reasons other than death or disease progression will be assessed at regular intervals for disease progression (approximately every 2 months through the first 6 months from the start of the subject's participation in this study and every approximately 12 weeks thereafter) and leukemic transformation (monthly blood counts). Disease assessments performed during the first 9 months from the start of the subject's participation in the study will include bone marrow evaluation. Thereafter, bone marrow evaluations will occur during disease assessments in accordance with institutional standard practice. These assessments will continue until disease progression, withdrawal of subject's consent to study procedures or initiation of another anticancer therapy.

All subjects will be followed-up for safety during treatment and up to approximately 30 days ( $30 \pm 7$  days) after treatment discontinuation or until immediately before the initiation of another anticancer therapy, whichever occurs first. Additional follow up may be implemented until the subject recovers from any emergent treatment related toxicity or the AE is considered irreversible by the Investigator. Target organ toxicities will be monitored via clinical and laboratory assessments using the NCI CTCAE v.4.03 criteria.

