## **8.6 Definition of End of Study**

For administrative and safety reporting purposes, the end of this clinical study is defined as the day when the last remaining study subject in the study completes the last follow-up assessment no later than 12 months after the last study subject is enrolled in the study. Provisions will be made for the continuation of study treatment in subjects whose disease has not progressed beyond the end of the study, e.g. a single patient treatment protocol.

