### **11.7.2 Follow Up after Disease Progression**

Upon disease progression, all subjects in the study will be followed approximately every 12 weeks for survival and the use of subsequent therapy until either death or 12 months after accrual of the study cohort has been completed, whichever occurs first. Information on survival and subsequent anticancer therapy may be collected by phone.

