10.3.4 Rate of survival at 1 year

Overall Survival (OS) will be defined as the time from date of the consent signed to the date of death due to any cause. Subjects who are alive or lost to follow-up by the end of study will be censored at the date of last known to be alive, which will be derived from the date reported in vital signs, laboratory, disease assessments, death, study discontinuation, and end of study CRFs. OS will be analyzed using Kaplan-Meier method. Rate of survival at 1 year, along with

the corresponding 95% confidence interval will be estimated in the same manner as 1-year PFS. Median survival with 95% confidence interval will also be reported.

The hazard ratio along with 95% CI (KRAS/NRAS WT vs KRAS/NRAS MUT, and CXCR4/2 High vs CXCR4/2 Low) will be estimated using a Cox proportional hazards model. The KRAS/NRAS MUT and CXCR4/2 Low will be used as the reference groups (ie, denominator of the hazard ratio). A time-to-event hazard ratio less than 1.0 would indicate an KRAS/NRAS WT benefit over KRAS/NRAS MUT or an CXCR4/2 High benefit over CXCR4/2 Low. Additionally, Log-rank P-value will be estimated using Kaplan-Meier method.

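### In cohorts that close before the last one, survival follow-up after the cohort date depends on progression, so overall survival beyond about 1 year and the CXCR4/2 hazard ratio can be biased

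*SAP*

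**What the plan says.** **Progressed subjects.** Protocol 11.7.2 follows them for survival about every 12 weeks "until either death or 12 months after accrual of the study cohort has been completed, whichever occurs first". Footnote 5 of the Schedule of Activities (Protocol Table 1) makes clear that this means the subject's own cohort: "until either death or 12 months after accrual in the subject's study cohort has been completed, whichever occurs first". SAP 5.2 repeats the rule.

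**Non-progressed subjects.** No cohort date is given.
- On treatment (Protocol 8.1): "In the absence of unmanageable toxicities, subjects may continue to receive tipifarnib treatment until disease progression".
- Off treatment without progression (Protocol 8.1): "These assessments will continue until disease progression, withdrawal of subject's consent to study procedures or initiation of another anticancer therapy".

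**End of study.** Protocol 8.6 sets it at study level, when the last remaining subject "completes the last follow-up assessment no later than 12 months after the last study subject is enrolled in the study".

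**Analysis.** SAP 10.3.4 states that subjects "alive or lost to follow-up by the end of study will be censored at the date of last known to be alive". It takes that date from forms that include vital signs, laboratory and disease assessments. From the same data it reports the 1-year rate, median survival with a 95% CI, Cox hazard ratios (RAS wild type vs mutant, CXCR4/2 high vs low) and log-rank P-values. No common OS cut-off is set.

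**The concern.** Kaplan-Meier, Cox and log-rank methods assume that a censored subject has the same later risk of death as those still under observation. In a cohort that closes early, this fails after the cohort date. Subjects already progressed are censored on that date. Subjects who progress later have no survival contact left and are censored near progression. Only the progression-free go on adding time. Progressed subjects are the ones expected to die sooner, so the late risk set is enriched with subjects at low risk and late mortality is understated.

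At stake are the OS curve beyond about 12 months, median OS if it lies well beyond 12 months, and the CXCR4/2 high-vs-low comparison. That comparison bears on the hypothesis behind amendment 3, and its two cohorts can close at different times.

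**Working it through.** **1. Inputs.** The documents give no event count, power or expected rate for OS, so there is no stated OS figure to reproduce. One design figure bears on closing times. The chance that a cohort stops at 7 subjects when the true ORR is 10% is 0.9^7 = 0.478, which matches the 0.48 in SAP 5.3.2. Unequal cohort sizes, and so unequal closing dates, are therefore likely under the design.

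**2. Length of the gap.** Let A_c be the date when a cohort's accrual ends and A_last the date of the last enrolment in the study. Progressed subjects are followed to A_c + 12 months, and others to at most A_last + 12. The gap is at most (A_last + 12) − (A_c + 12) = A_last − A_c. It is zero for the last-closing cohort and positive for the initial CMML cohort, which was enrolled before amendment 3. Its length is not stated.

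**3. When bias can start.** A subject entering at month e of an accrual period of a months has a + 12 − e months to the cohort date. This is at least 12, so the 1-year estimate is unaffected. It is at most a + 12. With 6-month accrual, no previously progressed subject is observed after month 18, and with 12-month accrual none after month 24.

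**4. Kaplan-Meier, 12-month accrual.** Illness-death simulation with exponential times and 200,000 subjects. Assumed medians: progression 6 or 9 months, survival after progression 6 or 12 months, death without progression 60 months.

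| Medians: progression / after | True 24-month OS | Gap 0 | Gap 6 | Gap 12 | Gap 24 | True median | Median read, gaps 6–24 |
|---|---|---|---|---|---|---|---|
| 6 / 6 | 0.20 | 0.197 | 0.252 | 0.262 | 0.261 | 13.0 | 13.1 |
| 6 / 12 | 0.385 | 0.386 | 0.421 | 0.427 | 0.428 | 18.9 | 19.4 |
| 9 / 12 | 0.445 | 0.448 | 0.495 | 0.502 | 0.506 | 21.4 | 23.5–25.1 |

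Twelve-month OS equalled the truth in every run (e.g. 0.688 vs 0.688). At 24 months the excess is about 4 to 6 points.

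**5. Shorter accrual.** Here 15% of first events are assumed to be deaths and the gap is 12 months. For medians 6/8 and 6/12, true 24-month OS is 0.27 and 0.38. It reads 0.41 and 0.49 with 6-month accrual, and 0.33 and 0.42 with 12-month accrual. A true median of 18.6 months reads 19.0 to 22.8. True medians of 12 to 15 months move by at most about 0.4.

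**6. Hazard ratios when there is no true difference.**

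| Comparison | Accrual assumed | As planned | One cut-off per cohort |
|---|---|---|---|
| RAS wild type vs mutant, same cohort | 12 months, gap 12 or 24 | 1.00 | 1.00 |
| CXCR4/2 high vs low | both 12 months, unequal gaps | 0.98–1.02 | – |
| CXCR4/2 high vs low | low 6, high 9–12 | 1.03–1.14 | about 1.0 |
| CXCR4/2 high vs low | low 6, high 18–24 | 1.10–1.32 | 0.99–1.01 |

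A separate set of runs with the last timing reached 1.38 at its extreme.

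**7. Against precision.** With 7 low and 18 high subjects, the simulations give about 2–4 and 4–14 deaths. The SE of the log hazard ratio is √(1/4 + 1/14) = 0.57 to √(1/2 + 1/4) = 0.87. Since ln 1.3 = 0.26, the shift is 0.26/0.87 = 0.30 to 0.26/0.57 = 0.46 SE. For 24-month OS of 0.385 at n = 18, the binomial SE is √(0.385 × 0.615/18) = 0.115, and censoring makes it larger. An excess of 0.04 is about a third of it.

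**The case against.** The case for leaving the plan alone has weight.

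- **The 1-year rate is the only OS quantity in the objectives** (Protocol 6.2, SAP 5.1.2), and it is unbiased. A reader might infer from the differing stop dates that it is distorted, but every subject has about 12 months of potential follow-up, so it is not.
- **The SAP does not name 24-month OS as an output.** It does report the median. The median OS of 11.7 months that Protocol 5.1.3 cites for a phase 2 MDS study of tipifarnib falls before any bias begins. Material error needs a true median of about 18 months or more.
- **The larger hazard ratios depend on timing.** High-cohort accrual of 18 to 24 months from March 2018 plus 12 months of follow-up runs to September 2020 to March 2021. The synopsis plans about 3 years from the second half of 2016. Shorter accrual gives 1.03 to 1.14.
- **Observation of non-progressed subjects to the end of study is inferred.** Protocol 8.1 and 8.6 do provide for continued treatment of subjects not progressed beyond the end of the study, which supports the inference. But new therapy or consent withdrawal ends assessment earlier, and end-of-treatment visits capture some deaths after the cohort date. Both narrow the asymmetry without removing it.
- **The quoted sentence is a standard last-known-alive rule.** The asymmetry comes from the protocol. The SAP is simply where it can be neutralised.

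These points limit the size of the problem. They do not supply a common cut-off.

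**Conclusion.** The point holds in limited form. In cohorts that close before the last one, the OS curve beyond about 12 months is biased upward, and so is a median of about 18 months or more. The CXCR4/2 hazard ratio and log-rank test can be biased when the two MDS/MPN cohorts close at different times. With no true difference the hazard ratio is about 1.0 to 1.3, a shift of less than half a standard error. These sizes rest on exponential event times and on assumed accrual periods and gaps that the documents do not give.

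Three stronger readings are not supported:
- **Both marker hazard ratios are distorted.** RAS wild type and mutant belong to the same initial CMML cohort with one cut-off. The ratio is unbiased when there is no difference, and the effect was small when the marker was assumed to delay progression from 6 to 9 months (0.82 vs about 0.84 with a common cut-off).
- **Every cohort is affected.** The last-closing cohort has no gap.
- **The rule favours the marker hypothesis.** If the low cohort closes first, the bias pushes the ratio above 1, against CXCR4/2 high.

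OS is a secondary endpoint without power or a decision rule. Severity is low to moderate.

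**What to change.** In SAP 10.3.4, replace the reference to the end of study with one OS cut-off per cohort: 12 months after completion of that cohort's accrual. Apply it to every subject regardless of progression. Subjects known to be alive at or after the cut-off are censored on that date, and later deaths and alive dates are not used. Use the same cut-off for the median, the Cox models and the log-rank test. As a sensitivity analysis, report OS with all recorded follow-up.

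The cost is one SAP sentence and one date per cohort, with no new data. Some late follow-up and deaths are dropped from the main analysis, and some medians may be reported as not reached.

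One related gap remains. The protocol writes no survival follow-up for subjects who start another therapy without progression. A cut-off date does not repair that, and the report should state how many such subjects there are.

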Determination of disease response in subjects with MDS/MPN will be performed by the Investigator according to the Myelodysplastic/Myeloproliferative International Working Group (MDS/MPN IWG criteria, Protocol Table 9). Similarly, disease progression will also be determined based on the MDS/MPN IWG criteria (Protocol Table 10). Determination of disease response in subjects with AML will be performed by the Investigator according to the International Working Group criteria (Cheson 2003). Similarly, disease progression will also be determined based on the IWG criteria (Cheson 2003).

Upon disease progression, all subjects in this study will be followed approximately every 12 weeks for survival and the use of subsequent therapy until either death or 12 months after accrual of the study cohort has been completed, whichever occurs first. Information on survival and subsequent anticancer therapy may be collected by phone.

Subjects who terminate treatment for reasons other than death or disease progression will be assessed at regular intervals for disease progression (approximately every 2 months through the first 6 months from the start of the subject's participation in this study and every approximately 12 weeks thereafter) and leukemic transformation (monthly blood counts). Disease assessments performed during the first 9 months from the start of the subject's

participation in the study will include bone marrow evaluation. Thereafter, bone marrow evaluations will occur during disease assessments in accordance with institutional standard practice. These assessments will continue until disease progression, withdrawal of subject's consent to study procedures or initiation of another anticancer therapy.

All subjects will be followed-up for safety during treatment and up to approximately 30 days (30 \pm 7 days) after treatment discontinuation or until immediately before the initiation of another anticancer therapy, whichever occurs first. Additional follow up may be implemented until the subject recovers from any emergent treatment related toxicity or the adverse event is considered irreversible by the Investigator. Target organ toxicities will be monitored via clinical and laboratory assessments using the NCI CTCAE v.4.03 criteria.

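### The overall-survival censoring date leaves out the 12-weekly survival contacts, so 1-year and median survival could be biased downward

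*SAP*

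**What the plan says.** SAP 10.3.4 defines overall survival as "the time from date of the consent signed to the date of death due to any cause". The censoring principle is: "Subjects who are alive or lost to follow-up by the end of study will be censored at the date of last known to be alive". The SAP then names the sources of that date, "which will be derived from the date reported in vital signs, laboratory, disease assessments, death, study discontinuation, and end of study CRFs". For estimation, "OS will be analyzed using Kaplan-Meier method", giving the 1-year rate and the median. The same section fits Cox models comparing the RAS groups and the CXCR4/2 groups.

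Protocol 11.7.2 says that after progression "all subjects in the study will be followed approximately every 12 weeks for survival and the use of subsequent therapy". This runs to death or, if that comes later, to one year past the close of the cohort's enrolment. It adds: "Information on survival and subsequent anticancer therapy may be collected by phone". SAP 5.2 repeats that subjects are "followed approximately every 12 weeks for survival and the use of subsequent therapy". Table 1 of the protocol gives this contact its own column and its own activity row. Protocol 8.4 and 11.6 place the End of Treatment visit about 30 days after the last dose.

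SAP 8 lists the reasons for leaving the study. They include completion, loss to follow-up and protocol-defined progression.

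**The concern.** The survival contact exists to measure this endpoint, yet it is not among the six named sources. A phone call produces no vital sign, laboratory or disease-assessment date. Once a subject has progressed and had the End of Treatment visit, a living status can enter the censoring date only through a study discontinuation or end of study form.

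Deaths have no such restriction. A death in month 11, learned by phone, is an event in month 11. A subject phoned alive in month 11, whose last clinic visit was in month 3 and who has no later exit date, is censored in month 3. Follow-up length then depends on outcome. Survivors leave the risk set early, deaths stay in, and the Kaplan-Meier curve falls too fast.

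One-year survival is a named secondary objective, and median survival uses the same dates.

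**Working it through.** The documents give no survival figure for this trial, so there is none to reproduce. The check covers the direction of the effect and its size over a range of assumptions.

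**1. Hand example (illustrative times).** Take one cohort of 18 (SAP 5.2). Nine subjects die, at months 2, 3, 4, 5, 6, 7, 8, 10 and 11; nine are alive past month 12. The Kaplan-Meier estimate is the product of (1 − deaths/at risk).

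- Full follow-up: 9/18 = 0.50.
- Cut *k* survivors back to month 5.5. Four deaths precede that time, leaving 14/18. Then 14 − *k* remain at risk and five more die, so S(12) = (14/18) × (9 − *k*)/(14 − *k*).
- *k* = 1: (14/18) × (8/13) = 0.48.
- *k* = 3: (14/18) × (6/11) = 0.42.
- *k* = 6: (14/18) × (3/8) = 0.29.

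No death was added or moved. Only the survivors' censoring dates changed.

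**2. Simulation.** From the documents: contacts every 12 weeks to 12 months after cohort accrual ends; End of Treatment visit about 1 month after treatment stops; cohort of 18; median survival of 11.7 months, taken from the prior MDS study in Protocol 5.1.3. Assumed, because the documents do not give them: exponential survival and progression, the median time to progression, the accrual pattern, and the share of living subjects with no date later than the last clinic visit.

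*Scenario A:* median survival 12 months; median PFS 4 months counting deaths, so progression alone has median 1/(1/4 − 1/12) = 6 months; potential follow-up 12 to 30 months. *Scenario B:* median survival 11.7 months, so true 1-year survival is 0.5^(12/11.7) = 0.491; median time to progression 4 months; uniform accrual over 12 months.

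| Share of living subjects cut back | A (true 0.50) | B (true 0.491) |
|---|---|---|
| 0% | 0.50 | 0.49 |
| 10% | 0.49 | 0.48 |
| 20% | – | 0.47 |
| 25% | 0.48 | – |
| 50% | 0.46 | 0.43 |
| 100% | 0.41 | 0.34 |

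**3. Sensitivity of the 100% row in B.**

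- Accrual over 24 months gives 0.39; over 6 months, 0.30.
- Median time to progression of 8 months gives 0.41 (and 0.46 when half are cut back).
- Median survival of 18 months (true 0.630) gives 0.46 or 0.54, for 4 or 8 months to progression.
- Median survival of 24 months (true 0.707) gives 0.52 or 0.61.
- Cohorts of 16 and 36 give the same pattern.

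**4. After the fix.** With all contact dates used, the mean estimate in B is 0.49 against 0.491. At medians of 18 and 24 months it is 0.63 against 0.630 and 0.70-0.71 against 0.707. No material bias remains.

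**The case against.** The sentence that omits the contacts also lists the study discontinuation and end of study CRFs, and its governing principle, last known alive, is the right one. Protocol 8.6 ties the end of study to the last follow-up assessment, and SAP 8 includes completion among the exit reasons. A subject followed alive to the end would therefore normally have an exit record. Survival follow-up runs to 12 months after cohort accrual closes, so each survivor has at least 12 months of potential follow-up and a completion date would usually fall past the landmark. For the 1-year estimate, any listed date past 12 months is enough; it need not be the last contact. The CRFs are not in the documents, so where contact dates are recorded is unknown, and the SAP does not say that the six sources are the only ones. The endpoint is secondary with no success rule, and cohort decisions rest on ORR. In a cohort of 18, the standard error at 50% survival is about √(0.25/18) = 12 points, far more than a bias of 1 or 2.

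Most of this stands, and it rules out two stronger readings. A reader might infer that the plan does bias 1-year survival downward, by some 9 to 15 points. That requires that no living subject has a later exit date, which the listed sources do not suggest. A reader might also infer that the biomarker hazard ratios are distorted. They use the same dates, but the direction and size depend on progression, survival and truncation in each group. The documents give none of these, and the effect was not computed.

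The objection does not close the gap. The SAP never says how exit forms are dated. Because progression is itself an exit reason in SAP 8, a form could be dated at progression, before any survival contact. An analysis run before exit forms are completed has the same weakness. A programmer given six named sources will probably treat them as the specification.

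**Conclusion.** The source list is incomplete and does not by itself secure the date that the SAP's own principle calls for. Downward bias in 1-year and median survival is possible, not demonstrated. Its size depends on a share the documents do not give: living subjects with no listed date after their last clinic visit. With true 1-year survival near 50% and the Scenario A and B assumptions, the loss is about 1 to 2 points if 10-25% are cut back and about 4 to 6 points if half are. Only the extreme case in which all are gives about 9 to 15 points, or more with short accrual (0.491 to 0.30 with 6 months). Slower progression makes it smaller: with 8 months to progression, about 3 points at half and 8 at all. There is no bias at 1 year if exit forms carry the last contact or any contact past 12 months. ORR and the two-stage decisions are unaffected.

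**What to change.** In SAP 10.3.4:

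- Add the survival follow-up contact date and any subsequent-anticancer-therapy date to the sources.
- Define last known alive as the latest date on which the subject was documented alive.
- Use dates from study discontinuation or end of study forms only when they reflect actual contact. An administrative closing date for a lost subject would credit survival nobody observed, and push the estimate upward.

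The cost is one SAP sentence and one more dataset in the derivation. The protocol already schedules collection of this information, so no visit or patient burden is added.
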